4.3 Justification for Dose

The proposed doses of M5049 for the study are 50 mg or 100 mg twice daily in a new tablet formulation without food restriction. The dose levels to be evaluated are selected based on safety, PK, and PD (inhibition of ex vivo-stimulated IL-6 cytokine secretion) observed in the single and multiple ascending dose (FIH) study in healthy participants. Pharmacokinetic results indicated dose-proportionality of maximal concentrations and overall exposure (AUC) in the investigated dose range (1 to 200 mg single or as daily dose) with a terminal half-life of 7 to 11 hours.

The following data were considered when determining the doses of M5049 for this study:

- Preliminary modeling and simulations based on the observed PK and PD (inhibition of ex vivo-stimulated IL-6 cytokine secretion) in the FIH study suggest that M5049 trough concentrations at steady-state ($C_{min,ss}$) will remain above the IC_{90} in 87.3% of the participants who receive a 100 mg twice daily dose and 31.2% of participants who receive a 50 mg twice daily dose. For both the 50 mg and 100 mg twice daily doses, M5049 trough concentrations will remain above the IC_{50} in more than 90% of participants.
- The FIH healthy volunteer study evaluated an oral M5049 solution under fasted condition except for a small food effect cohort. The current study will use a tablet formulation without food restriction. M5049 is considered as a Biopharmaceutics Classification System Class 1 compound and tablet formulation showed very rapid dissolution profile. It is expected that the new tablet formulation has similar exposure compared to the oral solution used in the FIH study.

- The expected $AUC_{0-24h,ss}$ and $C_{max,ss}$ at 100 mg twice daily without food restriction remains well below the exposures at the no observed adverse effect levels in 4-week nonclinical toxicology study in dog with at least 10-fold safety margin.
- The AUC was increased by 33% and C_{max} was decreased by 11% under fed condition compared to fasted conditions.

Based on the above considerations, both the 50 mg and 100 mg twice daily doses in the new tablet formulation without food restrictions may provide the opportunity to observe a PD effect (i.e., suppression of inflammatory biomarkers, e.g., IL-6) and clinical response in participants with COVID-19 pneumonia while also maintaining acceptable safety margin.

4.4 Early Hospital Discharge Assessments

A participant who is discharged from the hospital after Day 3 and before Day 14 should have the same assessments as ET of study treatments as per the schedule of assessments (Section 1.2), but continue study treatment as an outpatient until Day 14.

4.5 End of Study Definition

A participant has completed the study if he/she has completed all study parts, including the last visit or the last scheduled procedure shown in Table 1.

The end of the study is defined as the date of the last visit of the last participant or the last scheduled procedure shown in Table 1 for the last participant globally.

4.6 Early Termination of Treatment

When a participant is discontinued or withdraws from treatment before Day 14, the participant should complete the ET assessments as soon as possible and revert to the same study schedule (Table 1) based on the participant's Day 1; the participant should be encouraged to continue follow-up for safety and clinical assessments outlined in Table 1 through Day 60.

4.7 Surveillance, Safety and End of Study Visits

Since important secondary endpoints are evaluated at Day 28, surveillance assessments occur between Day 14 and Day 28, which may be distinguished from continued safety follow-up to Day 60. If a participant is discharged and not seen at the study site (as may be the requirement of the state and/or local hospital/clinic), every effort should be made to collect what information is available over the phone or through a telemedicine contact after hospital discharge.

As the majority of study participants should be discharged by Day 28, assessments for visits at Day 44 and Day 60 (End of Study) are anticipated to be by telemedicine or phone contact.

4.8 Relapse Definition

A participant who has been discharged from the hospital with an SpO₂ of $\geq 94\%$ sustained for at least 24 hours in room air, but who must be re-admitted before Day 60 due to worsening oxygenation (an SpO₂ $< 94\%$ in room air), with either a positive result of respiratory pathogenic nucleic acid test (NAT) or worsening lesions on chest imaging (compared to the participant's same modality of chest imaging [chest X-ray or computed tomography {CT}] at discharge, if available) will be counted as a respiratory relapse. For SARS-CoV-2 or any other infection, record the anatomic site from which the infection was assessed in addition to the infecting agent. The assessments in [Table 1](#) for the Relapse Visit will be performed, and assessments in [Table 1](#) will be resumed based on the participant's Day 1 of study entry.

5 Study Population

Hospitalized patients (≥ 18 to ≤ 75 years of age) with COVID-19 pneumonia not on mechanical ventilation with an SpO₂ $< 94\%$ in room air AND able to maintain a PaO₂/FiO₂ ≥ 150 (or equivalent SpO₂/FiO₂ ≥ 190) with a maximum FiO₂ 0.4. These readings may be obtained after exertion by the participant. Patients on continuous positive airway pressure should have assessments for eligibility performed while awake.

The correlation between SpO₂/FiO₂ ratio and measured PaO₂/FiO₂ ratio is high when restricted to patients with SpO₂ $\leq 96\%$, as substantial variation of PaO₂ is present in higher SpO₂ range ([Brown 2016](#)). The relationship between SpO₂/FiO₂ and PaO₂/FiO₂ was described by the following equation: $S/F = 64 + 0.84 \times (PaO_2/FiO_2)$ ([Rice 2007](#)). Maximum inhaled percentage oxygenation (FiO₂ 0.4) means patients should be on a nasal cannula or face mask without nonrebreather at ≤ 5 L/min (see guidance [Table 2](#)). (Note: face mask with nonrebreather will have a higher estimated FiO₂ [i.e., > 0.40] and therefore would be ineligible).

Table 2 Flow Rates Translated as Inhaled Oxygen Percentage (i.e., Fraction of Inspired Oxygen)

Device	Flow Rates	Delivered O ₂ ^a
Nasal cannula	1 L/min	21%-24%
	2 L/min	25%-28%
	3 L/min	29%-32%
	4 L/min	33%-36%
	5 L/min	37%-40%
	6 L/min	41%-44%
Simple oxygen face mask	6-10 L/min	35%-60%
Face mask with O ₂ reservoir (nonrebreathing mask)	6 L/min	60%
	7 L/min	70%
	8 L/min	80%
	9 L/min	90%
	10-15 L/min	95%-100%
Venturi mask	4-8 L/min	24%-40%
	10-12 L/min	40%-50%

a Percentage is approximate.

5.1 Inclusion Criteria

Participants are eligible to be included in the study only if all the following criteria apply during the 48-hour study Screening Period:

Informed Consent

- Participant (or legally authorized representative) provides signed informed consent prior to the initiation of any study assessments for participation in the study.

Age

- Are ≥ 18 to ≤ 75 years of age, at the time of signing the informed consent.

Type of Participant and Disease Characteristics

- Has laboratory-confirmed SARS-CoV-2 infection as determined by nucleic acid amplification test, polymerase chain reaction, antigen test, or other commercial or public health assay (based on locally accepted guidelines) in a sample collected < 10 days prior to randomization.
- Documentation of chest imaging consistent with COVID-19 pneumonia (as per locally accepted guidelines). If chest imaging is not available during Screening, please discuss with

Medical Monitor or designee regarding evidence of probable COVID-19 pneumonia for study participant eligibility.

5. Not on mechanical ventilation (invasive or noninvasive), or ventilation, or ECMO, nor (based on medical judgement of admitting physician) anticipated to be in the next 24 hours.
6. An SpO₂ < 94% in room air AND able to maintain a PaO₂/FiO₂ ≥ 150 (or equivalent SpO₂/FiO₂ ≥ 190) with a maximum FiO₂ 0.4. These readings may be obtained after exertion by the participant. Note: if participant is on chronic low O₂ therapy (≤ 2 L), assess their current baseline O₂ requirements for eligibility.
7. Requiring hospitalization (i.e., in the process of hospital admission or already admitted).

Birth Control based on Sex at Birth

8. a. Female Participants:

- Not a woman of childbearing potential (See [Appendix 2](#)).

OR

- If a woman of childbearing potential:

- Is using a depot contraceptive or extended cycle oral contraceptive from before the first dose of the study intervention(s).
- Agree not to become pregnant or donate eggs (ova, oocytes) for reproduction for a full 60 days.
- Use a highly effective contraceptive method (i.e., with a failure rate of < 1% per year) as described in [Appendix 2](#) for the duration of the study (a full 60 days), either with:
 - A daily use hormonal contraception from before the first dose of the study intervention(s),

OR

- Uses a barrier method during the length of the study (a full 60 days).

b. Male Participants:

- Agree to refrain from donating sperm for at least 90 days.

PLUS, either

- Abstain from intercourse with a woman of childbearing potential.

OR

- Use a male condom for at least 90 days:

When having sexual intercourse with a woman of childbearing potential, who is not currently pregnant, and advise her to use a highly effective contraceptive method with a failure rate of < 1% per year (see [Appendix 2](#)), since a condom may break or leak.

5.2 Exclusion Criteria

Participants are excluded from the study if any of the following criteria apply:

Medical Conditions

1. Any condition that could interfere with the study objectives, conduct or evaluation in the opinion of the Investigator or Sponsor or designee.
2. If pregnant (by positive high-sensitivity pregnancy test) or breastfeeding.
3. Clinically significant (i.e., active) cardiovascular disease: cerebrovascular accident/stroke (< 6 months prior to enrollment), myocardial infarction (< 6 months prior to enrollment), unstable angina pectoris, congestive heart failure (New York Heart Association Classification Class \geq III), or serious cardiac arrhythmia requiring medication (including corrected QT interval prolongation of > 470 ms and/or pacemaker) or prior diagnosis of congenital long QT syndrome. Note: documented, longstanding Left Bundle Branch Block (LBBB) resulting in a long QTc using Fridericia's formula, is not exclusionary if corrected by the QTc-LBBB $\{[QT - (0.7 \times QRS - 50)]/\text{square root RR}\}$ or JTc (QTc - QRS duration) formula.
4. History of uncontrolled illness (in the opinion of the Investigator) prior to SARS-CoV-2 infection, within the 3 months prior to Screening, including but not limited to:
 - a. Hypertension uncontrolled by standard therapies (not stabilized to 150/90 mmHg or lower), or
 - b. Uncontrolled active infection (e.g., septicemia), or
 - c. Significantly uncontrolled diabetes mellitus or any diabetes that has resulted in severe end organ damage, or
 - d. Uncontrolled or severe asthma or other chronic obstructive pulmonary disease. Note: uncontrolled asthma/chronic obstructive pulmonary disease is defined as more than 1 exacerbation in the previous 12 months that required an emergency room visit or hospitalization. Note: chronic low O₂ (\leq 2 L) therapy is allowed as long as the participant meets the criteria outlined in Inclusion Criterion 6.
5. History of epilepsy, other neurological disorder associated with seizures (e.g., cerebrovascular accident/stroke, acute brain infection, traumatic brain injury, progressive brain disease, congenital brain disease), or currently active and uncontrolled neuropsychiatric condition (in the opinion of the Investigator) including depression or current suicidal ideation.
6. History of interstitial lung disease prior to Screening or current thrombosis or embolism present during Screening.

7. History of a primary immunodeficiency, organ transplant, splenectomy or functional asplenia.
8. History of the following prior to Screening:
 - a. Human immunodeficiency virus infection.
 - b. Untreated hepatitis C (i.e., if hepatitis C antibody positive, hepatitis C DNA is detectable).
 - c. Untreated hepatitis B (positive for hepatitis B surface antigen or if hepatitis core antibody positive, hepatitis B DNA is detectable).
 - d. Recurrent herpes zoster (two or more episodes within a 10-year period).
 - e. Known active tuberculosis (TB) or untreated latent TB infection.

Note: laboratory confirmation of inactive infection status is not required for study eligibility. Appropriate TB test can be performed to diagnose TB infection per clinical judgement.
9. History of malignancy (hematologic or solid tumor) that is not currently under control or in remission prior to Screening.
10. History of known alcohol or drug abuse in the 3 months prior to Screening as per Investigator opinion.

Prior/Concomitant Therapy

11. Known hypersensitivity to any study treatment, component, or placebo.
12. History of vaccination against SARS-CoV-2. Vaccination is allowed after Day 28 as per local standard of care and/or as per the Investigator's clinical judgment and might be permitted before Day 28 after consultation with the Medical Monitor or designee.
13. Daily use of the following medications associated with serotonin syndrome within 14 days prior to randomization:
 - a. Antidepressants: selective serotonin reuptake inhibitors, serotonin norepinephrine reuptake inhibitors, tricyclic antidepressants, monoamine oxidase inhibitors, St. John's wort. Exception: fluoxetine within 8 weeks prior to randomization.
 - b. Analgesics: tramadol, fentanyl (i.e., intermittent use as needed prior to randomization is allowed).
 - c. Long-acting anti-emetics e.g., palonosetron, dolasetron. Short-acting anti-emetics, e.g, ondansetron, potentially associated with serotonin syndrome may be prescribed on an as needed basis. If short-acting antiemetics require around the clock administration for more than 1 day, please contact your Medical Monitor or designee to ensure safety of the study participant. Short-acting anti-emetics should not be administered within 3 hours of study treatment.
 - d. Linezolid, tryptophan, buspirone, tedizolid.
14. The initiation, use or change in therapies within 14 days prior to randomization:

- a. Use of raloxifene, tamoxifen, estradiol, clozapine, chlorpromazine (strong aldehyde oxidase inhibitors).
 - b. Use of corticosteroids exceeding 40 mg daily prednisone equivalent (e.g., dexamethasone 6 mg). Use of 40 mg daily prednisone equivalent (e.g., dexamethasone 6 mg) for more than 10 days during the study.
 - c. Any vaccination included but not limited to subunit or inactivated vaccines.
 - d. Use of Chinese herbal/non-herbal medications (e.g., tripterygium, total glucosides of peony, etc.).
 - e. Use of plasmapheresis or hemoperfusion (see Section 7.4.2).
15. The initiation, or use of therapies within 1 month prior to randomization:
- a. Vaccination with live or live attenuated virus vaccine.
 - b. Use of any medication considered to have immunomodulating and/or immunosuppressant properties including but not limited to the following: antimalarials, (e.g., chloroquine, hydroxychloroquine, mefloquine), leflunomide, methotrexate, 6-mercaptopurine, sulfasalazine, mycophenolate mofetil or sodium, azathioprine, cyclophosphamide, dapsone, retinoids, abatacept, anifrolumab, thalidomide, lenalidomide, anti-TNF α agents, systemic calcineurin inhibitors (e.g., cyclosporine, tacrolimus) (although topical use of calcineurin inhibitors are allowed), Bruton's tyrosine kinase inhibitors, other small molecules such as tofacitinib (i.e., Janus kinase/signal transducers, activators of transcription pathway inhibitors), IL-1 and IL-6 pathway inhibitors, TNF α pathway inhibitors, IL-12/IL-23 pathway inhibitors, (e.g., ustekinumab), or other disease modifying, immunosuppressive or immunomodulatory therapies not otherwise specified in protocol.
 - c. Use of B cell depleting/modulating therapy such as anti-CD20 agents including but not limited to rituximab, ocrelizumab, ofatumumab, obinutuzumab, ocaratuzumab, veltuzumab, or biosimilars thereof, belimumab, or dual or other anti-B Lymphocyte Stimulator/a proliferation inducing ligand neutralizing therapies (e.g., RCT 18).
16. Concurrent interventional clinical study participation prior to study randomization through Day 28. After Day 28, approval to participate must be requested from the Sponsor when there exists the intent of participation in a concurrent study.

Diagnostic Assessments

17. Clinically significant or predefined abnormalities in laboratory tests (serum chemistries: aspartate aminotransferase [AST], alanine aminotransferase [ALT] or alkaline phosphatase level $> 5.0 \times$ upper limit of normal [ULN]), or hematologic test (hemoglobin < 5.0 mmol/L [9 g/dL], white blood cells $< 1.5 \times 10^9$ /L, absolute neutrophil count < 750 /mm³, platelets $< 50 \times 10^9$ /L) at Screening.
18. Estimated glomerular filtration rate (eGFR) < 45 mL/min/1.73 m² as calculated by the Modification of Diet in Renal Disease equation:

$$\text{eGFR} = 175 \times (\text{serum creatinine in mg/dL})^{-1.154} \times (\text{age in years})^{-0.203} \times 0.742 \text{ (if female)} \times 1.212 \text{ (if race is black)}$$

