Appendix 4 Clinical Laboratory Tests

Laboratory Assessments	Parameters			
Hematology	Platelets		Mean Corpuscular Volume	WBC Count with Differential: 
 • Neutrophils • Lymphocytes • Monocytes • Eosinophils • Basophils
	Hemoglobin			
	Hematocrit			
Biochemistry	Blood Urea Nitrogen	Electrolytes (sodium, potassium, chloride, bicarbonate)	Aspartate Aminotransferase	Creatinine Kinase
	Creatinine	Albumin	Alanine Aminotransferase	Total Protein
	eGFR	Glucose		
Other Screening Tests	Serum hCG or urine pregnancy test (as needed for a woman of childbearing potential). All study-required laboratory assessments will be performed by local laboratory. It is required that these local laboratories are certified, perform and document interlaboratory testing at regular time intervals and provide a list of normal range laboratory values including units as defined by international system of units (e.g., CLIA-certified, UK NEQUAS, etc.).			
Baseline Tests	
 • Serum virology (hepatitis B and C screening, HIV) per local guidelines. • Urine drug screen per local guidelines. 			

CLIA = Clinical Laboratory Improvement Amendments of 1988; eGFR = estimated glomerular filtration rate; hCG = human chorionic gonadotrophin; HIV = human immunodeficiency virus; UK NEQUAS = United Kingdom National External Quality Assessment Service; WBC = white blood cell.

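### Exclusion criterion 17 prints 5.0 mmol/L and 9 g/dL as one haemoglobin limit, but they are about 0.9 g/dL apart

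*Protocol*

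**What the plan says.** Protocol 5.2, criterion 17, excludes candidates with "Clinically significant or predefined abnormalities in laboratory tests" at Screening and lists numeric cut-offs for serum chemistry and haematology. The haemoglobin entry is "hemoglobin < 5.0 mmol/L [9 g/dL"], with a single inequality sign covering both figures.

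Three other places bear on how a site would read it:

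- **Protocol Appendix 4** states: "All study-required laboratory assessments will be performed by local laboratory". It also asks those laboratories to supply their normal ranges in SI units.
- **Protocol 5.2, criterion 18**, the next criterion, uses a conventional unit: creatinine enters the eGFR equation in mg/dL.
- **SAP 9.6**, the only section on conversion factors, covers time, height and weight. It has nothing for haemoglobin.

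No other section of the Protocol or SAP sets a haemoglobin limit for eligibility or says which unit takes precedence.

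**The concern.** A value in brackets after a limit is normally read as the same limit in a second unit. Here the two values differ by more than rounding can explain, so the criterion gives two answers for one range of haemoglobin.

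This is a predefined numeric cut-off that decides whether a person may enter the trial. Testing is local, and SAP 8.2 lists three countries (United States, Philippines, Brazil). If some laboratories report in mmol/L and others in g/dL, the same patient could be eligible at one site and excluded at another. The documents do not say which units the sites use.

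Deviation review is affected too. SAP 10.2.1 has important deviations identified by site monitoring, medical review or programming. A programmed check on this criterion needs one threshold, and for someone enrolled at 8.5 g/dL the text does not settle whether there was a deviation.

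The treatment comparison is not at stake. Eligibility is settled before blinded allocation (Protocol 7 and 7.1), and no sample size, power or error-rate figure depends on this limit.

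**Working it through.** **Inputs.** From criterion 17: 5.0 mmol/L and 9 g/dL. The molar mass *m* of haemoglobin is not in the documents and is an assumption. The usual clinical convention is per monomer, *m* of about 16.114 g/mmol. A range of 16.0 to 16.5 is shown, deliberately generous at the upper end.

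**Formula.** g/dL = mmol/L × *m* / 10, and the reverse, mmol/L = g/dL × 10 / *m*.

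**The plan's own equivalence.** For 5.0 mmol/L to equal 9 g/dL, *m* would have to be 90 / 5.0 = 18.0 g/mmol, outside the assumed range.

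**Conversion of each figure.**

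| *m* (g/mmol) | 5.0 mmol/L in g/dL | 9 g/dL in mmol/L | Gap, g/dL | Gap, mmol/L |
|---|---|---|---|---|
| 16.0 | 8.00 | 5.63 | 1.00 | 0.63 |
| 16.114 | 8.06 | 5.59 | 0.94 | 0.59 |
| 16.5 | 8.25 | 5.45 | 0.75 | 0.45 |

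At the central value the gap is 0.94 / 9, or about 10% of the g/dL limit.

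**Could rounding explain it?** A value that rounds to 5.0 mmol/L is at most 5.05, and 5.05 × 16.5 / 10 = 8.33 g/dL at the top of the assumed range. A value that rounds to 9 g/dL is at least 8.5. The two intervals do not meet. With both figures at their most favourable rounding limits, equality would still need 85 / 5.05 = 16.8 g/mmol.

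**Could a tetramer basis explain it?** With *m* of about 64.458 g/mmol, 5.0 mmol/L is 5.0 × 6.4458 = 32.2 g/dL. That is further away, not closer.

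**Where the two limits disagree.** Below about 8.06 g/dL both figures exclude. At 9 g/dL and above neither does. Between them the figures conflict: 8.5 g/dL is 85 / 16.114 = 5.27 mmol/L, which is under 9 g/dL (excluded) but over 5.0 mmol/L (not excluded).

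**Candidate corrections at *m* = 16.114.**

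- 5.6 mmol/L is 9.02 g/dL, which matches 9 g/dL.
- 5.0 mmol/L is 8.06 g/dL, which prints as 8.1 to one decimal.
- 8 g/dL is 4.96 mmol/L, so printing 8 would leave a sliver from 8.00 to 8.06 g/dL unresolved.

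**The case against.** The arithmetic is hard to contest. The case on the other side concerns weight.

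- **Small and unquantified consequence.** Sites diverge only if they work in different units, which the documents do not state, and the number of candidates in the band is unknown. This is true, and it is why the point is a correction to make and not a threat to the trial's conclusions.
- **No visible haemoglobin risk.** The adverse events of special interest (Protocol 9.3.4) do not include anaemia, and the specific stopping rules in Protocol 8.1 set no haemoglobin level. The risk section is redacted, so whether 8.1 or 9.0 g/dL is the better limit cannot be judged from the documents. That stands as a reason for the sponsor to choose the limit. It does not excuse printing two.
- **Investigator discretion.** A candidate in the band can still be excluded under criterion 1, or for a clinically significant abnormality under criterion 17. This lessens any safety worry, but it does not say what the predefined limit is.
- **A default reading exists.** The mmol/L figure comes first and carries the inequality sign, and Appendix 4 leans towards SI units. However, Appendix 4 concerns normal-range lists, not eligibility. A site whose laboratory reports g/dL will naturally use the bracketed figure.
- **A single wrong digit.** A misprint or misread of 5.6 as 5.0 would produce exactly this mismatch. The limit appears only once, so nothing else in the documents can confirm or exclude that. The signed protocol is worth checking; if it also reads 5.0, the error is the protocol's.

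**Conclusion.** The concern holds. Criterion 17 gives two different haemoglobin limits as one, about 0.94 g/dL apart (0.75 to 1.0), or 0.59 mmol/L (0.45 to 0.63). The result rests on one assumption from outside the documents, a per-monomer mass between 16.0 and 16.5 g/mmol. No value in that range makes the figures agree, with or without rounding. The conflict is confined to roughly 8.1 to 9.0 g/dL; outside that band the criterion works. The error should be corrected because it sits in an operative eligibility threshold. Its practical frequency is unknown.

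**What to change.** The sponsor should confirm which limit is clinically intended, then print one correctly converted pair in criterion 17:

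- `< 5.6 mmol/L [9 g/dL]` if 9 g/dL is meant; or
- `< 5.0 mmol/L [8.1 g/dL]` if 5.0 mmol/L is meant.

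One figure changes. It can go out as a site clarification or in the next amendment; an amendment needs IRB/IEC approval before it is implemented (Protocol 11.1). It helps only candidates not yet screened. Any programmed deviation check on this criterion should use the confirmed limit. No new data collection or analysis is required.
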